The Effect Of Preoperative Parameters On Success After Descemet Membrane Endothelial Keratoplasty (DMEK) Surgery

CLINICAL STUDY PLAN

ClinicalTrials.gov Results Data Element Definitions for Interventional and Observational Studies

▼ 1. Participant Flow Enrollment Assessed for eligibility (n=) Excluded (n=) $_{\square}$ Not meeting inclusion criteria (n=) □ Declined to participate (n=) □ Other reasons (n=) Allocated to intervention (n=) Received allocated intervention (n=) Did not receive allocated intervention (give reasons) (n=) Follow Up Lost to follow Discontinued intervention (give reasons) (n=) Analysis Analysed (n=) Excluded from analysis (give reasons) (n=)

Groups/Cohorts	Interventions
Cohort	Procedure/Surgery: Descemet membrane endothelial keratoplasty
	(DMEK)
All patients	All participants underwent DMEK surgery

Period(s)

Our study was created by planning a 6-month follow-up period. Information about the number of patients at the beginning and end of the study will be reported when the study is completed.

▼ 2. Baseline Characteristics

Patients' age, gender, eye side, additional diseases, medications used and preoperative visual acuity values will be recorded at the beginning of the study.

Groups/Cohorts	Interventions
Cohort	Procedure/Surgery: Descemet membrane endothelial keratoplasty (DMEK)
All patients	All participants underwent DMEK surgery

Baseline Analysis Population Information

Overall Number of Baseline Participants

A total of 60 participants are planned to participate in the study.

Baseline Measure Information

Patients' age, gender, eye side, additional diseases, medications used and preoperative visual acuity values will be recorded at the beginning of the study.

Baseline Measure Title

The change in the visual acuity and the change in the number of endothelial cells will be the primary outcome of the study.

Study-Specific Measure *\sqrt{\sqrt{Select as many as needed}}

- Age (Select at least one of the following):
 - Age, Continuous: For example mean or median age
- Sex/Gender (Select at least one of the following):
 - Sex: Female, Male
- Race and Ethnicity
 - Race and Ethnicity Not Collected

Measure Type *

Definition: The type of data for the baseline measure. Select one.

• Count of Participants

Measure of Dispersion

Select one.

• Not Applicable (only if Measure Type is "Number", "Count of Participants", or "Count of Units")

Baseline Measure Data *

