The required sample size was determined by power analysis based on previous studies. [G * Power, Version: 3.1.9.2 Statistical Packages]. Variance analysis (ANOVA) will be used in the statistical analysis of preoperative and postoperative 1st and 6th months, if the measurements show normal distribution in the repeated measurements. Post-hoc Bonferroni test will be used to find out whether there is a difference between the measurements. Friedman test will be used in the statistical analysis of measurements that do not show normal distribution. Wilcoxon test will be used to find out whether there is a difference between the measurements. Pearson and Spearman correlation test will be used in the correlation analysis. For statistical significance p <0.05 will be accepted.

▼ 4. Adverse Event Information

Information for completing three tables summarizing adverse events.

- 1. All-Cause Mortality: Mortality is not expected in our study.
- 2. Serious Adverse Events: Serious adverse event is not expected in our study
- 3. Other (Not Including Serious) Adverse Events: No adverse effects due to study are expected. If any adverse event will be seen, it will be reported.

Time Frame

Adverse event data will be collected between 1 June 2019, and 1 June 2021.

Adverse Event Reporting Description [*]

Patients will be invited to examinations at regular intervals and will contact the researchers at the contact numbers provided if they see any unexpected effects.

Collection Approach for Table Default

• Systematic Assessment: Baseline and after surgery 1, 3, 6, and 12 months

Arm/Group Information

There is only a study group.

Arm/Group Title

All patients

Arm/Group Description

All participants underwent (Descemet membrane endothelial keratoplasty) DMEK surgery

Total Number Affected by All-Cause Mortality

Total Number at Risk for All-Cause Mortality

0

Total Number Affected by Any Serious Adverse Event

Total Number at Risk for Serious Adverse Events

0

Frequency Threshold for Reporting Other (Not Including Serious) Adverse Events

5

Total Number Affected by Any Other (Not Including Serious) Adverse Event Above the Frequency Threshold

Total Number at Risk for Other (Not Including Serious) Adverse Events $\boldsymbol{0}$

Adverse Event Term

A significant unexpected effect that affects the course of the study.

Organ System

• Eye Disorders

Collection Approach

• Systematic Assessment: Baseline and after surgery 1, 3, 6, and 12 months

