Number of Participants Affected

0

Number of Participants at Risk

0

▼ 5. Limitations and Caveats

Overall Limitations and Caveats

In our study, only Descemet membrane endothelial keratoplasty (DMEK) surgeries were included. However, Descemet's stripping automated endothelial keratoplasty (DSAEK) surgeries were not included, and no comparative study was performed.

▼ 6. Certain Agreements

Information indicating whether there exists an agreement between the sponsor or its agent and the principal investigators (unless the sponsor is an employer of the principal investigators) that restricts in any manner the ability of the principal investigators (PIs), after the completion of the study, to discuss the results of the study at a scientific meeting or any other public or private forum, or to publish in a scientific or academic journal information concerning the results of the study. This does not include an agreement solely to comply with applicable provisions of law protecting the privacy of participants.

Are all PIs Employees of Sponsor?

Definition: Indicate whether the principal investigator is an employee of the sponsor.

• Yes

PI Disclosure Restriction Type

There are no varying agreements.

▼ 7. Results Point of Contact

Point of contact for scientific information about the clinical study results information.

Name or Official Title *

Definition: [name] [name]

Organization Name *

Definition: Beyoglu Eye Research and Education Hospital

[contact]

[name]

Email: [contact]

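### Section 4 promises to report any adverse event seen but sets a unitless threshold of 5 for non-serious events, and it prints 0 participants at risk where 60 are planned

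*Combined protocol and SAP*

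**What the plan says.** All places are in the combined protocol and SAP.

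- **Promise.** Section 4, under other (non-serious) adverse events, says none are expected from the study and then: "If any adverse event will be seen, it will be reported".
- **Threshold.** Further down section 4, the field "Frequency Threshold for Reporting Other (Not Including Serious) Adverse Events" holds the figure 5, with no percent sign or other unit. The next field counts participants with a non-serious event above that threshold.
- **Number at risk.** For other events, section 4 prints 0 on the at-risk line. For the event term, the affected field and "Number of Participants at Risk" each carry their own 0. Under "Total Number at Risk for All-Cause Mortality" and "Total Number at Risk for Serious Adverse Events" a single 0 follows both the affected and the at-risk labels.
- **Size and exposure.** Section 2: "A total of 60 participants are planned to participate in the study". The group tables in sections 1 to 3 state: "All participants underwent DMEK surgery".
- **Period.** Section 4, Time Frame: "Adverse event data will be collected between 1 June 2019, and 1 June 2021". The same section twice gives a per-participant schedule: baseline, then 1, 3, 6 and 12 months after surgery. Section 1, Period(s), describes a 6-month follow-up.

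**The concern.** This is a single-arm surgical cohort. Apart from complications during the operation (section 3), section 4 is the only dedicated plan for adverse events, so postoperative safety reporting rests on it.

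Two things there do not fit. First, a promise to report any non-serious event cannot be kept by a table that lists only events above a frequency threshold, and the plan names no other place for events below it. In a cohort of 60, a threshold of 5 on either reading removes the infrequent events that a promise of full reporting would bring in. A reader of the finished table could not tell an event that never occurred from one that occurred in a few participants.

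Second, a denominator of 0 cannot be right for a group in which everyone is operated on. If it were carried into the results, a statement that no events were seen would come without an upper limit on the risk.

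**Working it through.** **Inputs**

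- Planned participants: n = 60 (sections 2 and 3), one group, all operated on.
- Threshold: 5, no unit (section 4). Both readings are carried: 5% and a count of 5.
- Rule: an event must be above the threshold (label of the affected field, section 4).
- True risks of 2%, 3%, 5% and 10%: illustrative assumptions, since the plan gives no expected event rates. Participants are treated as independent.

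**1. The plan's own figure.** With one group and everyone operated on, the number at risk equals the number operated on: 60 planned, not 0. The printed figure is not reproduced.

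**2. The threshold in participants**

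- As a percentage: 0.05 × 60 = 3. Three of 60 is exactly 5% and so not above it; at least 4 of 60 (6.7%) are needed.
- As a count: above 5 means at least 6 of 60 (10%).

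The largest result left out is therefore 3/60 = 5.0% (exact 95% CI 1.0% to 13.9%) on the first reading, and 5/60 = 8.3% (2.8% to 18.4%) on the second.

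**3. Chance that an event occurs, against the chance that it is tabulated.** With X ~ Binomial(60, p):

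| True risk p | P(X ≥ 1), occurs | P(X ≥ 4), above 5% | P(X ≥ 6), above a count of 5 |
|---|---|---|---|
| 2% | 0.70 | 0.03 | 0.001 |
| 3% | 0.84 | 0.11 | 0.009 |
| 5% | 0.95 | 0.35 | 0.08 |
| 10% | 0.998 | 0.86 | 0.56 |

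For p = 0.03 in full:

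- P(X = 0) = 0.97^60 = 0.161, so P(X ≥ 1) = 0.839.
- P(X = 0), …, P(X = 3) are 0.161, 0.298, 0.272 and 0.163, which sum to 0.894, so P(X ≥ 4) = 0.106.

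If the threshold included equality, the 3% row would read 0.27 (at least 3) and 0.03 (at least 5). The gap to 0.84 remains.

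**4. The denominator.** As printed, 0 affected of 0 at risk is 0/0, which is undefined. With 60 at risk and 0 affected, the exact two-sided 95% upper limit is 1 − 0.025^(1/60) = 0.0596, that is 6.0%.

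**The case against.** **The zeros are placeholders.** The document is a results template completed before there are results. Section 1 defers participant numbers to completion, section 2 does the same for baseline data, and the affected counts are also 0 before any could be known. This stands as the likely explanation. It does not remove the point: unlike sections 1 and 2, section 4 carries no note that its values are pending. An expectation of no events might explain 0 affected but not 0 at risk. For mortality and serious events the evidence is weaker, because one printed value follows two labels and text extraction may have dropped or shifted another. The point therefore rests on the other-events line and the event-term fields.

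**The threshold governs one table of non-serious events.** This is correct. It does not touch deaths, serious events or complications during surgery. It contradicts the promise only if that table is where non-serious events are reported, but the plan names no other place.

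**A reader might infer that no valid incidence can be derived.** The documents do not support that. The denominator is recoverable from sections 1 to 3, and section 4 gives a schedule per participant. A cumulative proportion can be computed once the 0 is replaced.

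**A reader might also infer from the calendar window that participants are followed unequally, for 12 to 24 months or, if operated on late, for less than 12.** Surgery after 1 June 2020 would indeed leave under 12 months inside the window. But no surgery dates are given, the dates fit 12 months of surgery plus 12 months of follow-up equally well, and scheduled assessment ends at 12 months for everyone. The documented problem with the period is the 6-month statement in section 1 against the 12-month assessments in sections 3 and 4.

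**Conclusion.** The point holds in a limited form. Section 4 is internally inconsistent on non-serious events. If 5 means 5%, events in up to 3 of 60 participants stay out of the table, and an event with a true 3% risk has about a 0.84 chance of occurring but about a 0.11 chance of being listed. If 5 is a count, events in up to 5 of 60 stay out and the chance of listing falls to about 0.009. These figures assume 60 operated participants, independence between them and the above-threshold rule; the 3% risk is illustrative.

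The number at risk of 0 contradicts the plan's own 60 and needs replacing, though it is probably an unfilled field and does not show that anyone intends to divide by zero. The correction matters for the precision of the safety statement. It has no bearing on the visual acuity or endothelial cell density analyses.

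**What to change.** 1. Set the threshold for other adverse events to 0, so that every non-serious event is tabulated as promised.
2. In every adverse event table, set the number at risk to the number who undergo DMEK (60 planned), or mark the field as pending until completion. Report each event as n/N with an exact 95% confidence interval.
3. State the adverse event period per participant, counted from surgery. This first requires the 6-month follow-up in section 1 to be reconciled with the 12-month assessments in sections 3 and 4.

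The first two changes are wording only, and the downside is a slightly longer adverse event table. The third needs a decision by the sponsor on which follow-up statement applies.
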